10.6.7 ECOG 18

11. Protocol Deviations 18

12. Listings 19

13. References 19

List of Abbreviations

Abbreviation	Term
AE	Adverse Event
ATC	Anatomical Therapeutic Chemical
BID	Twice Daily
CI	Confidence Interval
CLL	Chronic Lymphocytic Leukemia
CR	Complete Response
CT	Computed Tomography
CTCAE	Common Terminology Criteria for Adverse Events
DCR	Disease Control Rate
DoR	Duration of Response
DRC	Data Review Committee
ECG	Electrocardiogram
eCRF	Electronic Case Report Form
ECOG PS	Eastern Cooperative Oncology Group Performance Status
FAS	Full Analysis Set
IEC/IRB	Independent Ethics Committee/ Institutional Review Board
iwCLL	International Workshop on Chronic Lymphocytic Leukemia
MedDRA	Medical Dictionary for Regulatory Activities
mITT	Modified Intent-to-Treat
NCI	National Cancer Institute
ND	Not Done
NE	Not Evaluable
ORR	Objective Response Rate
PFS	Progression-Free Survival
PP	Per-Protocol
PR	Partial Response
PT	Preferred Term
Q1	First Quartile
Q3	Third Quartile
QTcF	QT interval with Fridericia's correction
SAE	Serious Adverse Events
SAP	Statistical Analysis Plan
SAS	Statistical Analysis Software
SD	Stable Disease
SOC	System Organ Class
TEAE	Treatment-Emergent Adverse Event
WHO	World Health Organization

1. Amendments from Previous Version(s)

Not Applicable.

2. Introduction

Note: [REDACTED]

This SAP provides the detailed methodology for summary and statistical analyses of the data collected in study RP6530-1901. This document may modify the plans outlined in the final protocol.

2.1 Rationale

Chronic Lymphocytic Leukemia (CLL) is a myeloproliferative neoplasm characterized by an accumulation of monoclonal mature B-cells (CD5+CD23+) in the blood, bone marrow, and secondary lymphatic organs. CLL is the most common form of adulthood leukemia.

Tenalisib is a highly specific and orally available dual PI3K δ/γ inhibitor with nano-molar inhibitory potency and several fold selectivity over α and β PI3K isoforms. Pre-clinical experiments demonstrated that Tenalisib is highly effective in killing primary CLL cells in vitro. The effect appeared to be equal to ibrutinib and higher than conventional chemotherapy agents. Tenalisib also demonstrated reduction in chemokine induced migration of Daudi cells, indicating its potential in modulating tumor microenvironment. Tenalisib has demonstrated clinical activity in patients with hematological malignancies with acceptable safety profile. Therefore, Tenalisib may offer a good treatment option for patient with relapsed/refractory CLL.

3. Study Objectives

3.1 Primary Objective

- *To assess the anti-tumor activity of Tenalisib as determined by the objective response rate (ORR) and duration of response (DoR)*

3.2 Secondary Objectives

- *To characterize safety and tolerability of Tenalisib*
- *To assess progression free survival (PFS)*

4. Study Endpoints

4.1 Efficacy Endpoints

- *Overall response rate (ORR): ORR is defined as sum of CR and PR rates as defined by iwCLL guideline for CLL (Hallek et al. 2018)².*

- *Duration of response (DOR): DOR is defined as the interval from the first documentation of CR/PR to first documentation of definitive disease progression or death from any cause.*
- *Progression-free survival (PFS): PFS is defined as the interval from first dose to first documentation of definitive disease progression or death from any cause.*

4.2 Safety Endpoints

- *Adverse Event (AE), Grade 3/4 AEs, Serious and fatal Adverse Event (SAE), graded using NCI CTCAE Version 5.0.*

5. Study Design

The trial is a Phase II, open label, Simon's two stage study design to evaluate the efficacy and safety of Tenalisib in 61 patients with CLL who have relapsed or are refractory after at least one prior therapy. In Stage 1, 20 patients will be enrolled and the study treatment Tenalisib (800 mg BID) will be administered orally in 28-days of cycle over a period of 7 months (C1D1 to C8D1) in absence of definitive disease progression or unacceptable toxicity. If 8 or fewer responders are observed in this stage, the study will be terminated. Else, 41 additional patients will be enrolled into stage 2.

Patients will be evaluated for efficacy response by CT at C3D1±7 days, C5D1±7 days and C8D1±7 days and/or at End of the treatment (EOT) visit. The study will end when all ongoing subjects have reached their third tumor assessment on Cycle 8/Day 1 (C8D1) or have discontinued from the study for any reason, whichever is earlier.

5.1 Study Stopping Rules

- **Safety:** *The Data review Committee (DRC) will continue to monitor safety of Tenalisib (or toxicity trends that may be of concern) at interval of approximately 3 months from initiation of study until the completion of the study. In the event of one (1) death attributed to the study drug, study accrual will be suspended pending further investigation, and will only be resumed at the recommendation of the DRC. In addition, the DRC may recommend for termination of the study in case of major safety concerns.*
- **Efficacy:** *Once 20 patients are recruited in stage 1 of the study, the DRC will review the efficacy results and may recommend early termination of the study if there are 8 or fewer responders out of 20 patients. Else, 41 additional patients will be enrolled into stage 2.*

In addition, Sponsor reserves the right to terminate the study in the interest of patient safety, for noncompliance with the protocol, lack of recruitment or any other administrative reasons. The sponsor and PIs will notify the regulatory authority and respective IRB/IEC respectively if the trial terminates early, with a justification for the early termination.

Notes:

- After reviewing the efficacy data, the study has been closed due to absence of clinically meaningful response to single agent Tenalisib in Stage 1 of the study. Therefore, Stage 2 will not be performed.
- The analysis proposed in this SAP is considering the available data at the time of completion of the study.

6. Sample Size Considerations

The sample size was derived based on Simon's two stage design to achieve 90% power at alpha of 0.05 for the null hypothesis of $ORR \leq 40\%$, assuming 60% response rate. Up to 61 patients will be enrolled. In stage 1, 20 patients will be enrolled, if 08 or fewer responders are observed in this stage, the study will be terminated without rejecting the null hypothesis. Otherwise, 41 additional patients will be enrolled into stage 2. If 31 or more responders are observed in the study, the null hypothesis of $ORR \leq 40\%$ will be rejected.

Stage 1: 21 patients with relapsed/refractory CLL is enrolled.

Stage 2 will not be initiated as the study is closed due to absence of clinically meaningful response to single agent Tenalisib.

7. Analysis Populations**7.1 Modified Intent-to-Treat Population (mITT) Analysis Set**

The mITT is the primary efficacy analysis population set and will include data from all patients who received at least 1 dose of study medication and provide at least 1 post-baseline efficacy assessment.

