9.3.3 Missing dates for Primary Diagnosis/Prior therapy

Partial Primary diagnosis and prior therapy dates will have imputation performed as explained below for the purposes of calculation of relativity to study medication.

- If only Day is missing, impute the day 1
- If Day and Month are missing, impute the Month as January and the Day as 1.
- If the year of primary diagnosis is missing or the date of primary diagnosis is completely missing, then no date will be imputed.

10. Statistical Analysis

Due to early closure of the study, the analysis proposed in the SAP is based on the available data at the time of study closure.

The safety endpoints will be listed and/or summarized. No inferential statistical analyses will be performed.

Unless otherwise stated, all statistical analyses will be performed using a two-sided hypothesis test at the overall 5% level of significance.

When count data are presented, the percentage will be suppressed when the count is zero in order to draw attention to the non-zero counts. A row denoted "Missing" will be included in count tabulations where necessary to account for dropouts and missing patients. Unless otherwise specified, the denominator for percentages will be the number of patients with a non-missing assessment in a given treatment group within the analysis population of interest.

All statistical analyses will be performed using SAS 9.4 or higher.

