10.1 Patient Disposition

A tabular presentation of the patient disposition data will be provided. It will include the number of patients screened, enrolled, assigned treatment, completed the treatment, as well as the number of dropouts, with reasons for discontinuation, number in each population sets, number of patients with dose reductions or interruptions (if applicable), etc. All patients' data will be used for this report.

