10.5 Efficacy Analysis

Analysis Set: mITT and PP

- These analyses will be done for overall population. }

Note: The analyses outlined below are subject to availability of adequate data. In absence of adequate data, some of the efficacy endpoints discussed below will be presented with basic summaries and/or plots and listings, as appropriate.

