10.5.1 Objective Response Rate (ORR)

It is defined as sum of CR and PR rates as defined by iwCLL guideline for CLL (Hallek et al. 2018)². Only those patients who have had a pre-treatment baseline efficacy evaluation and at least one post-treatment efficacy evaluation (that includes confirmed disease progression) will be considered evaluable for response. Overall ORR will be calculated.

Additionally, Disease Control Rate (DCR= CR+PR+SD) will be presented.

This data will be summarized using frequency, and percentage and the 95% CI (Using exact method based on binomial distribution, subject to availability of adequate data) for the Overall group.

The corresponding listing will also be provided.

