10.5.4 Best Overall Response

It is the best response, as assessed and confirmed by site PI, from the start of the treatment until disease progression or discontinuation from the study.

This data will be summarized using frequency and percentage for Complete Response (CR), Partial Response (PR), Stable Disease (SD), and Progressive Disease (PD), as reported in the CRFs for overall subjects.. This data will also be listed.

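### No efficacy analysis covers all treated patients: dropping unassessed patients can raise ORR and DCR but never lower them, early deaths fall outside PFS, and the status of deaths after end of treatment is unclear

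*SAP*

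**What the plan says.** SAP 7.1 (carried over from Protocol 9.3) defines the mITT set, the primary efficacy set: it "will include data from all patients who received at least 1 dose of study medication and provide at least 1 post-baseline efficacy assessment". SAP 10.5 heads the whole efficacy section "Analysis Set: mITT and PP", and SAP 7.2 makes PP a subset of mITT. The Safety Population (SAP 7.3) holds every dosed patient but is assigned only to safety. The FAS (SAP 7.4) serves demographics, baseline data, history, medications and deviations.

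SAP 10.5.1 and 10.5.2, following Protocol 8.1, repeat the restriction for ORR and for the CR and PR rates: besides a baseline evaluation, only patients with "at least one post-treatment efficacy evaluation (that includes confirmed disease progression) will be considered evaluable for response". The DCR sits under the same rule. By default in SAP 10, "the denominator for percentages will be the number of patients with a non-missing assessment in a given treatment group". Best overall response (SAP 10.5.4) names four categories, CR, PR, SD and PD, although NE and ND are in the abbreviation list.

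For PFS, SAP 4.1 and 10.5.5 count death from any cause. SAP 10.5.5 then adds that the end-of-treatment (EOT) visit is the cut-off for the PFS calculation. That sentence has no counterpart in Protocol 3.1 or 8.1, or in the DoR definition in SAP 10.5.3.

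There are safeguards. Confirmed progression counts as an evaluation. CT is planned at three visits "and/or at End of the treatment (EOT) visit" (SAP 5). A row for missing data "will be included in count tabulations where necessary to account for dropouts and missing patients" (SAP 10). Disposition reports the "number in each population sets" (SAP 10.1).

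**The concern.** Patients with no post-baseline assessment are likely to be those who died, had toxicity or withdrew before the first scheduled CT at C3D1 (study day 57, ±7 days). None of them can be a responder or have controlled disease. Excluding them removes failures from the denominator and nothing from the numerator, so the bias in ORR and DCR has only one possible direction.

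In PFS the plan conflicts with itself: death is an event, but a death before any assessment keeps the patient out of the analysed set.

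The cut-off sentence allows two readings. It may only fix which assessment dates the censoring of patients without an event. Or it may close the PFS clock at EOT, so that a recorded progression-free death after EOT is censored in PFS but still ends DoR. Two programmers could draw different curves.

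What is at stake is the reported estimates, not the decision to stop.

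**Working it through.** **The plan's own figure.** The inputs in SAP 9.1 are null ORR 40%, target 60%, stage 1 of 20 stopping at 8 or fewer, and rejection at 31 or more of 61. The exact probability of rejecting is the sum over x = 9 to 20 of P(X1 = x) × P(X2 ≥ 31 − x), with X1 ~ Bin(20, p) and X2 ~ Bin(41, p). It is 0.0487 at p = 0.40 and 0.9044 at p = 0.60, so the stated alpha of 0.05 and power of 90% reproduce. Both bounds are counts of responders, so the mITT denominator does not enter the rule.

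**Inputs for ORR and DCR.** 21 patients were enrolled (SAP 6). Assumption: all 21 were treated. The documents do not give the number of responders (r) or the number unassessed (k), so both are scenarios.

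**Direction.** mITT gives r/(21 − k); all treated gives r/21. The ratio is 21/(21 − k): 1.050, 1.105 and 1.167 for k = 1, 2 and 3. The mITT rate is never the lower one, and the two are equal only if r = 0 or k = 0.

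**Size**, with exact (Clopper-Pearson) 95% intervals:

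| Scenario | All treated, n = 21 | mITT, k = 1 (n = 20) | mITT, k = 3 (n = 18) |
|---|---|---|---|
| ORR, r = 0 | 0% (0–16.1) | 0% (0–16.8) | 0% (0–18.5) |
| ORR, r = 3 | 14.3% (3.0–36.3) | 15.0% (3.2–37.9) | 16.7% (3.6–41.4) |
| ORR, r = 8 | 38.1% (18.1–61.6) | 40.0% (19.1–63.9) | 44.4% (21.5–69.2) |
| DCR, 12 controlled | 57.1% (34.0–78.2) | 60.0% (36.1–80.9) | 66.7% (41.0–86.7) |

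The r = 8 row is the stage 1 stopping bound, so it is an edge case.

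**PFS, deaths before any assessment.** If k such deaths precede every other event and any censoring, the all-treated Kaplan-Meier curve is (21 − k)/21 times the mITT curve. At k = 1 an mITT value of 50% becomes 50% × 20/21 = 47.6%.

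A constructed example uses 18 assessed patients, with 4 events at day 57, 5 at day 113, 3 at day 197 and 6 censored at day 197, plus 3 deaths at day 30 before assessment:

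- Day 57: mITT 14/18 = 77.8%; all treated 14/21 = 66.7%.
- Day 113: mITT 9/18 = 50.0%; all treated 9/21 = 42.9%.
- Day 197: mITT 6/18 = 33.3%; all treated 6/21 = 28.6%.

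An unassessed patient with no recorded death would be censored at first dose and leaves the curve unchanged.

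**PFS, deaths after EOT.** Protocol 6.8 puts the EOT visit within 7 days of the last dose, or on the discontinuation date. Protocol 6.9 follows patients for 30 days after the last dose. That leaves 30 − 7 = 23 days, or up to about 30, in which a death can be recorded after EOT. Protocol 7.3.2 also has later deaths captured on the CRF. Counting one such death instead of censoring at EOT, with n patients at risk and no other event between EOT and the death, multiplies the curve from that day by (n − 1)/n: 14/15 = 0.933, 9/10 = 0.90 and 4/5 = 0.80 for n = 15, 10 and 5.

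**The case against.** The strongest reply is that few patients may be dropped. Protocol 8 lists physical examination and blood counts as part of the efficacy assessment, and Table 1 schedules both at C1D15, C2D1 and C2D15. If those qualify, only patients who leave before about day 15 are excluded and k may be near zero. If CT is required, the EOT visit also schedules one. Entry requires a life expectancy of at least 3 months. A reader could divide the responder count by the Safety Population size, deaths are summarised on that set (SAP 10.6.2), and listings show responses and withdrawals. The mITT set was fixed in the protocol, the trial is closed, and a shift from 14.3% to 15.0% changes no conclusion. The cut-off sentence never mentions censoring and follows text on the last tumor assessment, so it may only fix the censoring date.

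Much of this stands. The effect may be small or nil, stopping is unaffected, and prespecification is a reason to keep mITT. But SAP 7.1 does not say which assessment qualifies, so the reading that makes k near zero is not secured. The disposition counts, death summaries and listings let a reader find the gap, but supply no all-treated interval, DCR or PFS curve. The benign reading of the cut-off sentence is plausible but not stated.

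**Conclusion.** The concern holds and should be fixed. As written, the plan reports efficacy only for treated patients who were assessed; relative to counting unassessed patients as failures, this can raise ORR and DCR and cannot lower them. If all 21 enrolled were treated, the ORR is inflated by a factor of 1.05 with one patient dropped and 1.17 with three. With 3 responders and three patients dropped, the upper confidence limit moves from 36.3% to 41.4%, past the 40% null rate. With no responders, only the upper limit moves. DCR can shift more in points: 57.1% to 66.7% in the scenario shown.

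PFS is biased upward only where a dropped or cut-off patient has a recorded death. All these sizes are scenarios, because the documents give neither the responders nor the number unassessed; if no treated patient is unassessed, ORR and DCR are unchanged and only the post-EOT question remains for PFS.

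**What to change.** Keep the prespecified mITT and PP analyses, and make these changes:

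- **SAP 10.5:** add ORR, CR and PR rates, DCR and best overall response on the Safety Population, counting unassessed patients as non-responders and showing them in an NE/Missing row. State that this denominator overrides the non-missing default in SAP 10. Label the tables as added after efficacy data were reviewed, since SAP 5.1 records that review.
- **SAP 7.1:** state which post-baseline assessment qualifies a patient for mITT.
- **SAP 10.5.5:** add PFS on all treated patients, with a death before the first assessment as an event on its date and other unassessed patients censored at first dose. Reword the cut-off sentence so that the EOT assessment fixes only the censoring date of patients without an event. A recorded death without prior progression is then an event on its date in both PFS and DoR. PFS should not be truncated at C8D1.

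The cost is SAP wording and one extra table set, including a PFS curve. The data are already collected, and SAP 2 allows the SAP to modify the protocol's plans. The downside is that the added tables are post hoc relative to the efficacy review, and their ORR, DCR and PFS may be slightly lower than in mITT.

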7.2 Per-Protocol (PP) Population Analysis Set

The PP Population set is a subset of the modified Intent-to-Treat Population set and will include patients without major protocol deviations.

Major deviations shall include:

- Deviation from an IEC/IRB approved protocol which compromise the safety and welfare of participating subjects or the integrity of the study and /or the completeness, accuracy and reliability of study data. Examples of deviations included but not limited to:
 - Failure to obtain informed consent (e.g., there is no documentation of informed consent) for a subject;
 - Informed consent is obtained after initiation of study procedures;
 - Enrollment of subject who has failed to meet the inclusion/exclusion criteria.

The list of protocol deviations with categorization with respect to major and minor deviations will be generated prior to the study database lock. All deviations will be reviewed by the Medical monitor prior to database closure in order to decide whether to include the patient in a PP analysis population set. The PP population analysis set will also be used for efficacy assessment.

Note: If the patients qualifying for mITT set are same as the patients qualifying for PP set, the respective tables and figures proposed using PP set will not be produced to avoid the duplication of the results.

7.3 Safety Population Set

The Safety Population set will include all subjects who receive at least 1 dose of the study drug.

7.4 Full Analysis Set (FAS)

The FAS includes all the patients who sign the Informed Consent Document and are enrolled into the study. This set will be used for reporting patient demographic data and any available patient baseline characteristics as reported in the Case Report Form (CRF).

Membership in the analysis populations will be determined before database lock.

8. Randomization and Blinding

This is a non-randomized, open label study.

9. Method of Analysis

9.1 Statistical Hypotheses

The sample size was derived based on Simon's two stage design to achieve 90% power at alpha of 0.05 for the null hypothesis of $ORR \leq 40\%$, assuming 60% response rate. Up to 61 patients will be enrolled. In stage 1, 20 patients will be enrolled. If eight or fewer responders are observed in this stage, the study will be terminated without rejecting the null hypothesis. Else, 41 additional patients will be enrolled into stage 2. If 31 or more responders are observed in the study, the null hypothesis of $ORR \leq 40\%$ will be rejected.

9.2 Interim Analysis

No formal interim analysis will be performed for this study; however, the study data will be reviewed periodically by DRC during the course of the study. Refer Section 5.1 for detailed information.

9.3 Handling of Missing Data

9.3.1 Missing Dates for Adverse Events and Concomitant Medications

Adverse events and concomitant medications with completely or partially missing assessment dates will have imputation performed as explained below for the purposes of calculation of durations or relativity to study medication.

For the end of a concomitant medication or adverse event:

- **If only Day of end date is missing:**

The last date of the month and year reported or the date of the final contact with the subject, whichever is earlier, will be used as the end date.

- **If Day and Month of end date are missing:**

The last date of year i.e. December 31 of the year reported or the date of the last study contact with the subject, whichever is earlier, will be used as the end date.

- **If Year of end date or complete end date is missing:**

If the year of end of medication/event is missing or end date is completely missing, then no end date will be imputed.

For the start of a concomitant medication or adverse event:

- **If only Day of start date is missing:**

- If the start year and month of medication/event are the same as that for the first dose date, then following approach will be used:

- If the end date of medication/event is NOT before the first dose date or end date of medication/event is completely missing, then impute the start day as the day of first dose date
- Otherwise, impute the start day as 1.

- If the start year and month of medication/event are NOT same as that for the first dose date, then

- Impute the start day as 1.

- **If Day and Month of start date are missing:**

- If start year of medication/event is same as first dose year, then following approach will be used:

- i. For medication, impute the start Month as January and the Day as 1
- ii. For adverse event,

- If the end date of event is NOT before the first dose date or end date of event is completely missing, then impute the start Month and Day as the Month and Day of first dose date;
- Otherwise, impute the start Month as January and the Day as 1.

- If start year of medication/event is NOT same as first dose year, then

- Impute start Month as January and the Day as 1.

- **If Year of start date or complete start date is missing:**

If the year of start of medication/event is missing or start date is completely missing, then no start date will be imputed.

